CLINICAL STUDY PROTOCOL

PROTOCOL TITLE

**A DOUBLE BLIND, RANDOMIZED, PLACEBO CONTROLLED STUDY
TO EVALUATE EFFICACY AND SAFETY OF “VIRACIDE”
IN THE MANAGEMENT OF CORONA VIRUS DISEASE 2019 (COVID-19)**

**Protocol Number: NS-VC-CT01-20
Clinicaltrial.gov ID: NCT04596085**

STUDY SYNOPSIS

Title	A double blind, randomized, placebo controlled study to evaluate efficacy and safety of “ViraCide” in the management of corona virus disease 2019 (COVID-19).
Study Description	
This is a double blind randomized placebo controlled study will be conducted on 124 subjects, 50 years and older with mild or asymptomatic COVID-19. If symptomatic, symptoms are mild (cough, weakness, sore throat, low grade fever 38.50C, respiratory rate should not be more than 22 / min, resting SpO2 >95%, normal highly sensitive C-reactive protein (HS-CRP) (<10mg/L). There are no signs of dehydration, sepsis or shortness of breath.
 
The study will be conducted at two centers. There will be a screening visit at Day -4 followed by three visits at the center at Days 1, 7 and 15 and a follow-up visit on Day 28. All participants will be randomized to receive either ViraCide (investigational product) or matching placebo. All subjects will receive SOC therapy.
 
Note: If subject is discharged before Day 15 PI’s discretion as per patients health condition, then assessments scheduled for Day 15 will be carried out on the discharge day (as far as possible and those not performed will be noted on appropriate CRF page) and Day 15 visit will be done telephonically.

Investigational Product/Study drug	ViraCide softgels given per orally
Comparison product	Matching placebo of ViraCide softgels given per orally
Study Design	Double blind, randomized, placebo controlled study. Subjects will be randomized to the experimental and control groups in a 1:1 ratio. In each group 62 subjects will be recruited, a total of 124 subjects. Subjects of the experimental arm will receive treatment with Study Drug, ViraCide and SOC. The control group will receive matching placebo and SOC. The study consists of the stages of screening, therapy, observation. There will be no switching of subjects between the arms. Participants will receive Study drug or matching placebo for 14 days during the study.
Sample Size	124, including 10% dropouts
Study Population	
 • 50 years or older • Positive RT- PCR for Sars-Co-V2. • Either asymptomatic or have mild symptoms. Onset of symptoms within no more than 4days • With chronic stable medical conditions: Diabetes Mellitus, or Hypertension, or chronic heart disease.
Study Duration	Total study duration approximately 35 days Screening: 04 days Treatment duration: 14 days Follow-up: 14 days from end of treatment

Number of Sites	02 (two)
Treatment Duration	14 days
Treatment Arms	
Two treatment arms
 
 • Arm A: ViraCide softgels: 3 soft gels, two times every day after breakfast and dinner for 14 days+ SOC Therapy • Arm B: Placebo softgels: 3 soft gels, two times everyday after breakfast and dinner for 14 days + SOC Therapy
Purpose of the study	To study the effectiveness and safety of the Study Drug, ViraCide
	softgels by oral administration compared with placebo softgels in 50 years or older subjects with asymptomatic or mildly symptomatic coronavirus infection (COVID-19) and stable comorbidities.
Objectives	
Primary Objectives
 
1. To evaluate the efficacy of “ViraCide” in the management of mild COVID-19 disease
 
Secondary Objectives
 
1. To evaluate the safety of “ViraCide” in the management of mild COVID-19 disease

Primary Endpoints	
1. TICI using NEWS Score [Time Frame: First treatment date up to discharge day (PI's discretion as per patients health condition)]
 
The median time in days from the start of treatment with the study drug / placebo to the persistent achievement of all of the following criteria:
 
 • Stopping a fever (which is defined as a decrease in axillary temperature below 37 ° C without the use of anti pyretic drugs); • Respiratory rate <22 /min; • Oxygen saturation (SPO2) > 95% when breathing in atmospheric air. Measured using pulse oximetry • Systolic blood pressure ≤200mmHg • Pulse rate 51-90beats/minute • Is conscious and alert 
[Note: Persistent achievement means the preservation of each of the criteria for at least 7days.]
 
2. TTIC using 7-point ordinal scale
 
3. Rate of progression to severe/critical COVID-19 disease based on NEWS score [Time frame: First treatment date up to 15days]
 
4. Rate of progression to severe/critical COVID-19 disease based on 7-point ordinal scale [Time frame: First treatment date up to 28days]
 
5. Time to COVID-19 nucleic acid testing negativity in oropharyngeal/nasal swab) [Time Frame: First treatment date up to 28days]

Secondary Endpoints	
 1. Incidence of ICU admissions [Time Frame: 28days] 2. Subject survival rate [Time Frame: 28days] 3. Incidence of mechanical ventilation due to COVID-19 infection [Time Frame: First treatment date up to 28days] 4. Change in clinical or laboratory assessment of comorbid condition [Time Frame: First treatment date up to 28days] 5. Percent of participants with worsening comorbid condition [Time Frame: First treatment date up to 28days] 6. Proportion of subjects in the treatment arm who had AE, SAE 7. Proportion of subjects in the placebo arm who had AE, SAE
Subject Selection Criteria	
Inclusion criteria
 
 1. 50 years or older
	
 2. Both male and female subjects will be included 3. Positive oropharyngeal/nasal swab RT-PCR for Sars-Co- V2. Diagnosed not more than 2 days ago (diagnosis ≤ 2 days). 4. Either asymptomatic or have mild symptoms. Onset of symptoms within no more than 4 days. If symptomatic, symptoms are mild (cough, weakness, sore throat, low grade fever 38.50°C, respiratory rate should not be more than 22 / min, resting SpO₂ $>95\%$, normal highly sensitive C-reactive protein (HS-CRP) ($<10\text{mg/L}$). There are no signs of dehydration, sepsis or shortness of breath. 5. Chronic stable medical conditions: diabetes mellitus, or hypertension, or chronic heart disease. Under treatment and controlled by medication 6. Signed informed consent/or consent given through text message, WhatsApp or e-mail. 7. Ability to understand the requirements of the Research Protocol and follow the research procedures. 8. Subject should be willing to be managed in isolation wards 9. Negative pregnancy test (for female participants) 10. Adequate contraception for study duration 
Exclusion criteria
 
 1. Less than 50 years 2. With severe COVID-19 symptoms requiring immediate hospitalization 3. Investigator considers the subject unsuitable for ViraCide 4. History of symptoms of more than 4 days 5. COVID-19 diagnosed >2 days ago using oropharyngeal/nasal swab RT-PCR for Sars-Co-V2 6. History of cardiopulmonary resuscitation

	
 7. Subjects having history of organ failure or conditions requiring ICU monitoring and treatment, such as severe liver disease, severe renal dysfunction, upper gastrointestinal hemorrhage, disseminated intravascular coagulation or any other condition that in the PI's opinion makes the subject unfit to participate 8. Respiratory failure, ARDS or need of mechanical ventilation 9. History of acute exacerbation of comorbidity like heart failure, diabetic ketoacidosis, myocardial infection, major cardiac rhythm disorder or any other condition that in the PI's opinion makes the subject unfit to participate 10. History of or current hepatic failure or severely compromised liver function, or renal failure or having chronic kidney disease or acute renal failure 11. History of or currently receiving treatment for an endocrine disorder like hypothyroidism, hyperthyroidism that is likely to affect the basal heart rate. 12. History of or currently under treatment for asthma [exception: patients with history of asthma, not on medications/inhalers/nebulizers for at least 6 months
	
before study start), COPD, bronchiectasis, asbestosis and other such chronic lung conditions that can compromise SpO₂ and RR.
 
 13. HIV, HBsAg, HCV positive 14. Any condition causing immunodeficiency 15. Systemic connective tissue disease or any autoimmune disease that is likely to affect HS-CRP levels 16. History of epilepsy/epileptic fit/convulsions in last 6 months or currently on treatment for it 17. History of or currently having malignancy and being treated for it. (exception: histologically confirmed and cured carcinoma in situ) 18. Hypersensitivity reaction to Study drug/placebo 19. Any psychiatric issue for which the subject is currently undergoing treatment 20. Any history of drug/alcohol dependence within 30 days of screening or current drug/alcohol dependence 21. Inability to understand the requirements of the Research Protocol and follow the research procedures. 22. Pregnant or lactating; 23. Not willing to use adequate contraception during study duration 24. Participation in any other clinical study less than 3 months before the start of the study.
Stopping the Study Drug	
 1. Completing 14 days of treatment 2. Progression to severe COVID-19: ViraCide will be stopped if subjects progresses to severe COVID-19 and require ICU admission, mechanical ventilation and any such situation where according to the PI the subject

	
cannot continue ViraCide. However, subject will be followed-up to capture data on ICU admission, incidence and mortality
 
 3. Progression of comorbid condition requiring admission to ICU or inability of the subject to take anything orally. However, subject will be followed-up to capture data on ICU admission, incidence and mortality 4. Subject's participation to the study is terminated 5. Study is terminated
Termination of Subject's Participation in the Study	
Any participant can be removed from the study:
 
 1. By his/her own free will to not continue in the study. Subject withdrawal of informed consent. 2. Loss of contact with the subject during the study. 3. Does not comply with dosing schedule (75%-125% non-compliance) 4. The development of AE / SAE requiring the withdrawal of the study drug. However all AE / SAE will be followed-up till the study duration 5. Pregnancy confirmed anytime during the study duration 6. Another reason, which, according to the PI, requires the termination of the subject's participation in the study.
Study Termination	
The study can be terminated if
 
 1. There is a major deviation in Protocol 2. Another reason, which, according to the PI, requires study termination
Visits of Assessment	
Screening and 3 visits and one telephonic follow-up
 
Screening Inclusion/Exclusion Criteria, Subject Inform Consent, Demography, Medical History, Physical Examination, Vital Signs, HIV; HBsAg; HCV; Hs-CRP; Pulse oximetry; NEWS scoring; 7- point ordinal scoring; Medication list review (medications being taken for comorbid conditions), Lab assessment; Urine analysis Note: Patients who do not meet the study inclusion exclusion criteria during screening should not be randomized into the study.
 
Day 1 Randomization, Vital Signs, Pulse oximetry, AE/SAE, Concomitant Medication, ViraCide/ Placebo treatment start, NEWS scoring; 7-point ordinal scoring
 
Day 7 Physical Examination, Vital Signs, AE/SAE, Concomitant Medication, ViraCide/ Placebo Compliance check, Pulse oximetry; NEWS scoring; 7-point ordinal scoring. (Note: If the subject is discharged on this day as per PI's discretion and patient's health condition then assessment scheduled for day 15 will be carried out on discharge day).
 
Day 15 Physical Examination, Vital Signs, AE/SAE, Concomitant Medication, ViraCide/ Placebo treatment end, RT-PCR for

	
Sars- Co-V2, Hs-CRP, Safety Lab Tests, Pulse oximetry; NEWS scoring; 7-point ordinal scoring, ViraCide/ Placebo Compliance check, Lab assessment including urine analysis
 
Day 28 Phone call follow up for time :
 
 • until negative RT-PCR for Sars-Co- V2, COVID-19 related mortality, • development of any COVID-19 symptom, • development of any worsening of comorbid condition; • Development of new AE/SAE; Resolution status of previous AE/SAEs 
Note: If subject is discharged before Day 15 on PI's discretion as per patients health condition, then assessments scheduled for Day 15 will be carried out on the discharge day (as far as possible and those not performed will be noted on appropriate CRF page) and Day 15 visit will be done telephonically.

Laboratory Investigations	
Screening: Recording RT-PCR- Sars-Co-V2 result; Urine pregnancy test; HIV; HBsAg; HCV; Hs-CRP; Hematology* + Biochemistry + Urine analysis*; ECG
 
Day 1: No labs
 
Day 7: No labs
 
Day 15: Oropharyngeal/nasal swab for PCR- Sars-Co-V2; Hematology* + Biochemistry + Urine analysis*; ECG; Serological biomarker: Hs-CRP

	
Note:
 
*Hematology: Complete blood count (CBC); erythrocyte sedimentation rate (ESR)
 
*Biochemistry:
 
 • Random Blood Sugar, • Serum Creatinine • SGOT, SGPT • Alkaline Phosphatase • Bilirubin-Total/Direct/Indirect • Total Proteins/Albumin/Globulin/A:Gratio • Low density lipoprotein (LDL) Cholesterol(Direct) • LDH • Total Cholesterol • Triglycerides • High Sensitive C-reactive protein(HS-CRP) • BUN (Blood Urea Nitrogen) /Urea • Serum Calcium • Serum Sodium • Serum Potassium • Uric Acid 
*X-ray PA view is an optional test at screening. It may be done

	
at any other time during the study if deemed necessary by the Investigator
 
*Urine pregnancy test (for females only) at screening
 
Note: If subject is discharged before Day 15 PI's discretion as per patients health condition, then assessments scheduled for Day 15 will be carried out on the discharge day (as far as possible and those not performed will be noted on appropriate CRF page) and Day 15 visit will be done telephonically.

Standard of Care Therapy	
SOC therapy for coronavirus infection (COVID-19, SARS-CoV-2) has not been developed yet. Treatment will be given as per the discretion of the PI or as per the guidelines issued by the GOI. GOI guidelines can be accessed here: https://www.mohfw.gov.in/

Concomitant Medications Allowed by the Protocol	
 1. Medications for Diabetes Mellitus 2. Medications for hypertension 3. Statins 4. Blood thinners like aspirin at PI discretion 5. Any medication deemed necessary by the PI to manage the AE/SAE 6. Any other medication deemed necessary by the PI to manage a comorbid condition that is not likely to affect the treatment Protocol
Prohibited Concomitant Medications	Any other herbal medicine or dietary supplement
Statistical Analysis	
Sample size of total 112(56 cases in each arm) completed cases needed to assess the study objective at 80% power and 5% level of significance.
 
Considering 10 % dropout total 124 (62 cases in each arm) cases will be enrolled in this study.

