STATISTICAL ANALYSIS PLAN

STUDY TITLE:

A DOUBLE BLIND, RANDOMIZED, PLACEBO CONTROLLED

STUDY TO EVALUATE EFFICACY AND SAFETY OF

“VIRACIDE”

IN THE MANAGEMENT OF

CORONA VIRUS DISEASE 2019 (COVID-19)

Version No. – 01

Dated: 04th June 2020

Protocol ID – NS-VC-CT01-20

Clinicaltrial.gov ID: NCT04596085

Confidential & Proprietary

the unauthorized use, disclosure, distribution or copying of these information is strictly prohibited

Confidential

Page

1 of 11

Table of Contents

[1 Definitions](#)

[2 Objectives](#)

[3 Analysis Sets](#)

[4 Data handling](#)

[5 Statistical methods](#)

[5.1 Descriptive methods](#)

[5.2 Primary analysis](#)

[5.3 Analysis of the secondary endpoints](#)

[5.4 Safety and/or further analyses](#)

[6 Listings, tables, figures](#)

[7 Graphs](#)

[8 Software](#)

Confidential & Proprietary

the unauthorized use, disclosure, distribution or copying of these information is strictly prohibited

Confidential

Page

2 of 11

1 Definitions

The following abbreviations will be used in this statistical analysis plan.

ITT	Intention-to-treat
PP	Per protocol
IP	Investigational product
AE	Adverse Event
SAE	Serious adverse event
TTCI	Time to clinical Improvement
SPO2	Oxygen saturation
ICU	Incentive Care Unit

Confidential & Proprietary

the unauthorized use, disclosure, distribution or copying of these information is strictly prohibitea

2 Objectives

Primary Efficacy Endpoint:

1. TICI using NEWS Score [Time Frame: First treatment date up to when PCR is negative]

The median time in days from the start of treatment with the study drug / placebo to the persistent achievement of all of the following criteria:

- Stopping a fever (which is defined as a decrease in axillary temperature below 37 ° C without the use of antipyretic drugs);
- Respiratory rate <22 / min;
- Oxygen saturation (SPO2) > 95% when breathing in atmospheric air. Measured using pulse oximetry
- Systolic blood pressure ≤200 mmHg
- Pulse rate 51-90 beats/minute
- Is conscious and alert

[Note: Persistent achievement means the preservation of each of the criteria for at least 7 days.]

2. TTIC using 7-point ordinal scale
3. Rate of progression to severe/critical COVID-19 disease based on NEWS score [Time frame: First treatment date up to 28 days]
4. Rate of progression to severe/critical COVID-19 disease based on 7-point ordinal scale [Time frame: First treatment date up to 28 days]

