5. Time to COVID-19 nucleic acid testing negativity in oropharyngeal/nasal swab) [Time Frame: First treatment date up to 28 days]

Confidential & Proprietary

The unauthorized use, disclosure, distribution or copying of these information is strictly prohibited

Secondary Efficacy Endpoints:

1. Incidence of ICU admissions [Time Frame: 28 days]
2. Subject survival rate [Time Frame: 28 days]
3. Incidence of mechanical ventilation [Time Frame: First treatment date up to 28 days]
4. Time to COVID-19 nucleic acid testing negativity in oropharyngeal/nasal swab) [Time Frame: Days 1, 7, 15]
5. Change in clinical or laboratory assessment of comorbid condition [Time Frame: First treatment date up to 28 days]
6. Percent of participants with worsening comorbid condition [Time Frame: First treatment date up to 28 days]

Safety Endpoints

1. Proportion of subjects in the treatment arm who had AE, SAE
2. Proportion of subjects in the placebo arm who had AE, SAE

Confidential & Proprietary

Any unauthorized use, disclosure, distribution or copying of these information is strictly prohibited

3 Analysis sets

Per protocol subset (PP)

Subjects without any Major protocol violation would be included in the per-protocol population, including those subjects who have completed all the visits, who did not take any prohibited medications during the study period and whose CRF was completed as requested.

Modified Intention to treat subset (mITT)

The term “mITT” includes all randomized subjects who met all inclusion/exclusion criteria, administered at least one dose of assigned product with at least completed one visit will be included in the mITT population.

Safety analysis subset

The safety population will consist of all subjects enrolled in the study, who have received at least one dose of study products i.e. mITT population.

Methods of Analysis

Primary Efficacy and secondary endpoints will be analyzed using the PP & mITT population. And Safety variables as per mITT only.

4 Data Handling

Data entry into CRF must be performed as per general CRF data entry guidelines, summarized at the time of data entry feasibility training. Data entry will be made as per source document without interpretation or modification to maintain consistency and accuracy of the data. Study specific

Confidential & Proprietary

Any unauthorized use, disclosure, distribution or copying of these information is strictly prohibited

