5.1 Descriptive methods

Participant Disposition

Demographic and Baseline Information

Continuous variables that are Age, weight, BMI, and other demographical characteristics will be summarized by overall using summary statistics i.e. the number of observations, mean and standard deviation with 95% CI (among normal distribution) or median with range (if non-normal distribution). Categorical values like gender and clinical Examination will also be summarized using frequencies and percentages.

Confidential & Proprietary

Any unauthorized use, disclosure, distribution or copying of these information is strictly prohibited

The medical history and Physical examination will be presented using frequencies and percentages of subjects for the Safety population. For continuous data student analysis of variance test and for categorical data Chi square test will be estimated to compare the baseline demographical data between groups and changes during the follow up.

5.2 Efficacy Parameters:

Summary of efficacy parameters – the number of observations, mean and standard deviation with 95% CI (among normal distribution) or median with range (if non-normal distribution)

Analysis of Primary Efficacy Parameters

In this study median Time to Clinical Improvement (TTCI) using NEWS Score [Time Frame: First treatment date up to when PCR is negative] TTIC using 7-point ordinal scale [Time Frame: First treatment date up to when PCR is negative] will be assessed for both Test and Placebo group and compare the mean time between two arms by using Mann Whitney U test.

Other variables that are Rate of progression to severe/critical COVID-19 disease based on NEWS score and 7 point ordinal scale [Time frame: First treatment date up to 28 days] will be compared by using Chi Square test.

Other parameter like Time to COVID-19 nucleic acid testing negativity in oropharyngeal/nasal swab) [Time Frame: First treatment date up to 28 days] will be estimated by Student t test or one way analysis of variance. If data is

Confidential & Proprietary

Any unauthorized use, disclosure, distribution or copying of these information is strictly prohibited

not passing normality for continuous variable Mann Whitney test will be assessed instead of student t test.

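### Protocol and SAP set different windows for two NEWS-based primary endpoints, and no rule scores subjects discharged fewer than 7 days after first meeting the TTCI criteria

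*Protocol*

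**What the plan says.** **TTCI by NEWS (primary endpoint 1).** The protocol synopsis, Primary Endpoints, gives "TICI using NEWS Score [Time Frame: First treatment date up to discharge day", with discharge left to the investigator according to the subject's condition. SAP section 2 gives "TICI using NEWS Score [Time Frame: First treatment date up to when PCR is negative", and section 5.2 repeats it: "median Time to Clinical Improvement (TTCI) using NEWS Score [Time Frame: First treatment date up to when PCR is negative". Both documents require all six criteria to be kept for at least 7 days.

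**Progression by NEWS (primary endpoint 3).** The protocol has "based on NEWS score [Time frame: First treatment date up to 15days". SAP section 2 has "Rate of progression to severe/critical COVID-19 disease based on NEWS score [Time frame: First treatment date up to 28 days", and sections 5.2 and 6 also say 28 days.

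**Schedule.** Protocol, Visits of Assessment, lists NEWS at screening and Days 1, 7 and 15. If a subject leaves before Day 15, the Day 15 assessments move to the discharge day and Day 15 becomes a telephone contact. Discharge on Day 7 is expressly foreseen. The Study Description calls Day 28 a follow-up visit, but Visits of Assessment defines it as a phone call. That call asks about time "until negative RT-PCR for Sars-Co- V2" and about symptoms, comorbidity, deaths and adverse events; NEWS is not listed.

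**PCR.** After baseline, the protocol schedules a swab only at Day 15 (or discharge) and no laboratory tests on Day 7. The SAP's fourth secondary endpoint and its table list have "Time to COVID-19 nucleic acid testing negativity in oropharyngeal/nasal swab) [Time Frame: Days 1, 7, 15".

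**Analysis.** For TTCI, SAP section 5.2 says to "compare the mean time between two arms by using Mann Whitney U test". SAP section 4 (Data Handling) covers CRF entry and site records only. Neither document says how to score a subject whose 7-day persistence was not observed.

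**The concern.** Two of the five primary endpoints have different definitions in two current documents, so the analyst must choose between them. The more serious problem is the combination of a 7-day persistence rule, an observation period that can end at discharge, and a rank test with no rule for unobserved outcomes. Discharge depends on how well the subject is, so missing confirmation is related to recovery. A subject who first meets all six criteria on Day 7 and goes home that day could be given a time of Day 7, left out, or ranked with those who never improved. These choices give different rank orders on the first-listed primary endpoint. If treatment affects time to discharge, the choice can also move the between-arm comparison. As the plan stands, the choice could be made after the data have been seen.

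**Working it through.** The plan states no figure for this point, and the sample size plays no part in it. The check is a comparison of texts followed by day arithmetic.

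**1. Windows side by side**

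| Endpoint | Protocol | SAP | Last scheduled NEWS |
|---|---|---|---|
| TTCI by NEWS | to discharge | to negative PCR | Day 15 or discharge |
| Progression by NEWS | 15 days | 28 days | Day 15 or discharge |

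Progression: 28 − 15 = 13 days (Days 16-28) have no scheduled NEWS. Both windows therefore contain the same scheduled scores, and the label is what differs.

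TTCI: on the protocol's swab schedule, the first post-baseline PCR falls on the day of the last NEWS, so both windows again contain the same scheduled scores. They part in two cases.
- A subject still positive at the last swab has an SAP window that stays open with no further NEWS scheduled.
- If a Day 7 swab were taken, as the SAP's secondary endpoint implies, a negative result would close the SAP window on Day 7. Then 7 − 1 = 6 elapsed days, so no onset could be confirmed inside it (only Day 1 onset if days are counted inclusively). The protocol window would stay open to discharge.

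**2. Persistence by discharge day**

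Inputs: NEWS on Days 1 and 7 while in hospital and on discharge day d; 7-day rule. Assumptions: confirmation must fall inside the window, and no vital signs are measured after discharge. An onset on day a is confirmable if d − a ≥ 7 (elapsed) or d − a ≥ 6 (inclusive). The latest confirmable onset is therefore d − 7 or d − 6.

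| Discharge day | Elapsed, scheduled NEWS only | Elapsed, daily ward readings count |
|---|---|---|
| 2-7 | none (at most 7 − 1 = 6) | none |
| 8 | Day 1 | Day 1 |
| 9-13 | Day 1 | Day 1 up to Day d − 7 (Day 2 to Day 6) |
| 14 | Day 1 or Day 7 | Days 1-7 |

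Inclusive counting moves each limit one day earlier: none for discharge on Days 2-6; Day 1 onset from discharge on Day 7; Day 7 onset from discharge on Day 13.

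Discharge on Days 2-7 (elapsed) or 2-6 (inclusive) thus allows no confirmation, whether or not ward readings count. For later discharges the answer depends on onset day and on which readings count.

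**3. Subjects who stay to Day 15**

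The same limit applies at the end of the schedule: 15 − 7 = 8, so an onset after Day 8 (Day 9 inclusive) cannot be confirmed either. The missing rule is not only about discharge.

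**4. Worked case**

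All six criteria first met on Day 7, discharged Day 7: 7 − 7 = 0 days observed. The text gives no value, rank or censoring time for this subject.

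**The case against.** A reader might infer that early-discharged subjects can never meet the persistence rule. The documents do not support that. Asymptomatic subjects are eligible, and symptomatic ones enter with mild disease and resting saturation above 95%, so some may meet all six criteria on Day 1. Such a subject discharged on Day 8 or later satisfies the rule.

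A reader might also count calendar days. On 12 of the 13 possible early-discharge days (Days 2-14) no onset after Day 1 is confirmable, or 11 of 13 inclusively. That assumes only scheduled NEWS counts. Subjects are managed in isolation wards, and if daily readings count the figure is 7 of 13 (Days 2-8), or 6 of 13 inclusively (Days 2-7). Either way these are days, not subjects, and they say nothing about how many people are affected.

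Third, 13 of 28 days (46%) without NEWS might be taken as lost data. It is not: the 15-day and 28-day windows use the same scheduled scores, so this is a labelling conflict.

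Fourth, the TTCI window conflict changes the scheduled data only if a Day 7 swab is taken, which the protocol does not schedule. That is fair, but the SAP lists one, and the two texts still define the endpoint differently.

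Last, the window might limit onset only, with confirmation allowed later. Then the Day 28 question about new symptoms has some bearing. But only telephone contacts are scheduled after discharge, and they do not measure saturation, pulse, blood pressure or respiratory rate. The gap remains.

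**Conclusion.** The concern holds in limited form.

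- The windows for TTCI by NEWS and progression by NEWS conflict between two current documents. For progression the effect is a 28-day label that the schedule does not support.
- Seven-day persistence cannot be shown for anyone discharged fewer than 7 days after first meeting the criteria. This includes every discharge on Days 2-7 by elapsed counting, or Days 2-6 inclusively. It does not include every early discharge.
- The SAP gives no rule for these subjects, so some early recoverers have no valid TTCI for the Mann-Whitney test. This scoring gap is the part that must be fixed before analysis.

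The day limits rest on confirmation falling inside the window and on no vital signs being measured after discharge. The number of subjects affected, and the direction and size of any bias, cannot be computed, because the documents give no distribution of discharge or onset days.

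**What to change.** 1. **Progression by NEWS.** Set the window to Day 15 in SAP sections 2, 5.2 and 6. State that for subjects who leave earlier NEWS is observed only to discharge.
2. **TTCI window.** Use one window in both documents that does not end at PCR negativity, for example Day 1 to Day 15. Reconcile the PCR schedule between the protocol's Visits of Assessment and Laboratory Investigations rows and SAP sections 2 and 6.
3. **Day count.** State whether 7 days is elapsed or inclusive, and whether ward readings between visits count.
4. **Scoring rule.** Before unblinding, fix one rule for every subject whose persistence cannot be observed, the same in both arms. Label it as imputation. An early-discharged subject who is unobserved to Day 15 should not be treated as a proven failure. If the rule uses the Day 15 telephone contact, say what that call records for this purpose.
5. **Sensitivity analyses.** (a) Score these subjects as not achieved. (b) Censor them at their last NEWS and use a method for censored times, such as the log-rank test, because the Mann-Whitney U test cannot use censored values.

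The cost is wording in both documents and two extra analyses. No visits are added and discharge decisions are untouched. The drawback is that persistence is partly imputed and censoring at discharge is informative. None of the analyses is free of bias, so they should be read together.
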